[name], former Assistant Secretary of DHHS, has proposed a Health Literate Care Model based on the chronic care model.^{30,31} The model encourages both patients and providers to be activated and engaged and suggests that improving health outcomes relies on patients' full engagement. Our strategy, in combination with PCMH standards achieved by each clinic, and previous clinic training by [name] in implementing health literacy strategies recommended in the Agency for Health Care Quality and Research's (AHRQ) Health Literacy Universal Precautions Toolkit³² address many of the attributes included in this model: 1) assuming all patients are at risk of not sufficiently understanding their disease or self- management; 2) providing clear communication following plain language principles and easy to read, culturally appropriate materials, 3) confirming and ensuring patients understand via the '*teach back*' technique, 4) providing close follow-up with patients using a health coach, 5) incorporating provider health literacy training and point-of-care clinical reminders for medication reviews, 6) use of an electronic health record (EHR) to track progress. *We will use health coaches to ensure constant patient engagement and provide the tools necessary to frequently monitor action plans and performance.*

Hypothesis and/or Specific Aims or Objectives

The primary aims and hypotheses are to:

1. Test the effectiveness of the ACP diabetes health literacy intervention to improve a range of diabetes-related outcomes among rural patients.

Compared to enhanced usual care, patients receiving ACP intervention will demonstrate:

- H_1 greater disease and treatment knowledge H_2 higher self-efficacy to manage diabetes H_3 greater adherence to self-care behaviors H_4 less diabetes-related distress H_5 improved diabetes-related quality of life H_6 better disease control (HbA1c, blood pressure)
- 2. Compared to usual care, evaluate whether the intervention reduces disparities by patient literacy level.

H₇ Limited health literacy will be associated with the above health outcomes in the enhanced usual care arm, but not in the intervention arm.

[figure not shown]
- 3. Investigate whether a threshold or gradient effect exists between the amount of follow-up counseling (number of action plans) and intervention effectiveness.

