- 4. Determine the fidelity of all intervention components, and explore any identified patient, provider (physician, nurse, health coach), and/or health system barriers to implementation.
- 5. Assess the costs associated with implementing the ACP intervention from a health system perspective.

Study Design and Procedures

We will conduct a 2-arm, patient-randomized, pragmatic trial among 750 patients in Arkansas with type 2 diabetes to test the effectiveness and fidelity of a multifaceted, health coachled, low literacy, self-management intervention to improve behavioral and clinical outcomes compared to enhanced usual care in level 3 patient centered medical homes. Enhanced usual care differs from standard diabetes care because enhanced usual care includes patient resources associated with PCMH (team-based care, electronic health records, and care coordination). Eligible, consented patients will be followed for 1 year post baseline interview. Those receiving the ACP intervention will be administered the ACP health literacy strategy at baseline, with 'frontloaded' telephone or in-person follow-up education approximately every 3 months, counseling and action-planning occurring at approximately 2 weeks, 4 weeks, and 8 weeks and then monthly between guarterly clinical visits. In-person, 'point-of-care' counseling sessions will occur guarterly, coinciding with diabetes routine clinical visits. We intentionally aimed to optimize the number of 'touch points' over 1 year, taking into account a reasonable workload for health coaches. Addressing Aim 3, which seeks to ascertain the minimum number of action plans necessary to achieve clinical diabetes goals, or an increasing benefit is seen with more touch points (no threshold). Primary outcomes include intermediary biomarkers indicative of proper disease selfmanagement (HbA1c, blood pressure, LDL cholesterol). In addition, secondary outcomes to be measured include diabetes and treatment-related knowledge, self-efficacy, disease-related distress and quality of life, activation, health behaviors and health services utilization. To determine the reliability and costs associated with delivering the intervention, we will also closely monitor the implementation process and evaluate the fidelity of the components and strategies.

		hanced Usual Care and Intervention
	STANDARD	DIABETES MEDICAL CARE
		In Both Arms
Care Management	of medical care	rting
		AND SELF-MANAGEMENT SUPPORT
	'Enhanced" Usual Care Arm	Intervention Arm

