Follow-Up	 Follow-up at scheduled clinic visits approximately every 3 months No standard, practices vary over time 	 In-person 15 min education & counseling sessions at approximately 3,6, 9, and 12 months with health coach Phone calls with health coach to inquire about progress on action plans, use motivational interviewing to problem-solve or establish new action plans Bi-weekly post-visit phone calls for first 3 months (2,4, and 8 weeks after baseline encounter) Monthly post-visit phone calls between clinic visits after 3 months (4,5,7, 8, 10, and 11 month calls) Survey data will be collected at baseline, 3 and 6 months; clinical data will be collected following baseline, 3, 6, 9, and 12 months
Clinical Integration	 Documentation in EHR with nursing note whether post visit DM counseling occurred (yes or no) and when 	 EHR tools and prompts for health coach follow-up phone calls or face-to-face meetings, documentation of call attempts Health coach received information on patients' glycemic control (HbA1c lab value at visit) prior to patient counseling session Health coach documents in EHR every month using care note function: describes and provides update for PCP detailing patient's diabetes action plans and progress towards goals Email to PCP via EHR if patient does not complete 2 consecutive action plans, identifying barriers is known, or if any concerns arise

Figure 1. Study flow chart

Study Sites

The project will engage six UAMS Regional family medicine clinics in regions of Arkansas that are underserved and rural. All clinics have implemented the Patient-Centered Medical Home (PCMH) model of care and achieved the highest level of accreditation, level 3. All regional medical centers have participated in implementation of health literacy best practices using the Agency for Healthcare Quality and Research (AHRQ)'s Health Literacy Universal Precautions Toolkit for the last two years. The majority of patients served by these clinics is low-income and there is a high rate of chronic disease in each clinic's patient population. There are approximately 2,205 total patients at these clinics with HbA1c greater than 7.5%, which denotes that an individual has perhaps not yet achieved tight glycemic control and therefore may be at elevated risk for diabetes-related complications. All clinics have agreed to participate. Letters of support from the clinic directors are included.

Preliminary Studies

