The two-day training developed by Drs. [name], [name] and [name] will be informed by previous staff training in community clinics using the ACP guide and brief counseling framework. The session will take place in a central location and will include discussion of roles and responsibilities of the health coach for this project, and a review of the counseling framework. Skill-building will focus on brief education and coaching to facilitate patients' setting health goals and creating highly specific and easily achievable action plans. Training will also include skill building in motivational interviewing, clear communication and use of health literacy best practices (slowing down, using plain language, reducing numeracy demands, pointing out key messages in the guide book and using teach-back to confirm understanding). The theory-based training is designed to improve health coaches' capacity to enhance patients' understanding of their disease and problem-solving ability to change their health behavior and adhere to their action plans. The training will also focus on effective telephone counseling and follow up, employing strategies developed in previous research to reach patients by phone. Instruction will also be provided on use of a tracking system to recorded number of contacts (phone and in person), length of time spent in each contact, number of attempts to reach patients, and the content of each session.

Nurse training will cover an overview of the usual care diabetes materials in the enhanced usual care arm only (the "Living Well with Diabetes: a self-care workbook"). A review of the standards for usual care delivery will be provided to avoid contamination, as well as training on the tracking system. This will be provided by the Director of Research for the family medical centers in collaboration with the study team.

Randomization. After the initial phone call to recruit participants, the RA will assign patients interested in participating to either the intervention or to the enhanced usual care arm based on an allocation table created prior to study recruitment using a simple 1:1 randomization scheme, stratified by site. Patients will receive a \$30 Walmart gift card at baseline, a \$30 Walmart gift card at 3 months and a \$30 Walmart gift card at 6 months for their participation. If the patient has a phone call for the 3 month follow-up, they can get their gift card the next time they come into clinic

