where *i* corresponds to the individual subject (*i*=1,...,*total N*), β_0 serves as an intercept, β_1 serves as the intervention effect [*I*(*ACP intervention*_i) is an indicator variable for active ACP intervention arm], β_2 represents the effect of baseline value of the corresponding outcome variable, and ϵ_i represents random error. Primary analyses will test the null hypothesis H_0 : $\beta_1 = 0$ against the twosided alternative at the 5% level of significance. Similar analyses will be employed for all relevant outcomes at three and/or six-month follow-up (to examine efficacy/effectiveness) and 12-month follow-up (to examine sustainability). Baseline variables (demographics, comorbidities, health literacy, etc.) will be explored one at a time, in turn, for association with outcome(s), and where appropriate, models will adjusted for significant baseline prognostic variables. Exploratory analyses will employ linear mixed effects models that include a fixed treatment arm, baseline value, relevant prognostic variables, and time effects along with a random subject effect in order

to account for within-subject association among outcome observations. Exploratory analyses will involve inclusion of a fixed change-point or spline term(s) to examine changes in slope over different time periods and/or higher order/interaction terms. In order to examine whether there may a difference across clinic, a random clinic effect will be examined as well, and where appropriate, subgroup analyses by clinic will be employed.

To address Aim 2 (H₇), the subjects will be classified by literacy level (lower literacy or higher literacy), and above analyses will be repeated within each arm but include an indicator for literacy group. Further, the primary model (above) will be modified to include a literacy level effect and corresponding arm-by-literacy level interaction term.

To address Aim 3, we will analyze only those subjects randomized to the ACP intervention arm. We will examine association of (a) number of contacts with each subject and (b) length of contact time, with each relevant outcome variable (H_1 - H_6) at follow-up via a linear model as above. Each model will include an intercept, baseline value for the relevant variable, and variable (a) and/or (b), along with any additional demographics/prognostic variables found relevant in Aims 1 and 2.

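### Aim 3 asks about the number of action plans, but its only planned analysis uses contacts and contact time, so it cannot give a minimum number of plans

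*Combined protocol and SAP*

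**What the plan says.** All references are to the combined protocol and SAP.

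- **Hypothesis and/or Specific Aims or Objectives, Aim 3:** "Investigate whether a threshold or gradient effect exists between the amount of follow-up counseling (number of action plans) and intervention effectiveness". The parenthesis defines the dose.
- **Study Design and Procedures:** Aim 3 "seeks to ascertain the minimum number of action plans necessary to achieve clinical diabetes goals". The alternative is that "an increasing benefit is seen with more touch points (no threshold").
- **Data Analysis, Aim 3 paragraph:** in the intervention arm only, "We will examine association of (a) number of contacts with each subject and (b) length of contact time, with each relevant outcome variable". Each linear model holds an intercept, the baseline value and "variable (a) and/or (b), along with any additional demographics/prognostic variables found relevant in Aims 1 and 2".
- **Study design table, Follow-Up row, intervention arm:** on calls the coach asks about progress and is to "use motivational interviewing to problem-solve or establish new action plans".
- **Study design table, counseling row:** a new plan is identified if the patient rates confidence or importance at 7 or below.
- **Preparation phase, coach training:** the tracking system records "number of contacts (phone and in person), length of time spent in each contact, number of attempts to reach patients", and also session content.
- **Fidelity outcomes:** from the coach logs the study documents whether the patient was reached and the time spent.
- **Study design table, Clinical Integration row:** coaches write a monthly EHR note on plans and progress, and email the primary care provider after two consecutive uncompleted plans.

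**The concern.** The exposure named in the aim is not the exposure in the model. A coefficient per contact or per minute cannot be turned into a number of action plans without knowing how many plans a contact produces, and the documents do not say.

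Aim 3 is one of five stated aims, and action plans are central to the protocol's account of how the intervention works. If the plan is followed exactly, the final report can describe benefit per contact and per minute, but it has no basis for a statement about how many plans are needed. If a plan count is added only later, its definition (set or completed, up to when, from which source) could be chosen after outcomes are known.

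**Working it through.** **1. Compare the exposure in the aim with the exposure in the model.**

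| Place | Exposure |
|---|---|
| Aims, Aim 3 | number of action plans |
| Study Design and Procedures, threshold half | minimum number of action plans |
| Study Design and Procedures, gradient half | touch points |
| Data Analysis, Aim 3 model | number of contacts; length of contact time |

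The analysis paragraph lists all its model terms, and none is a plan count. The touch-point row is matched by the model. The first two rows are not.

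**2. Are the two counts the same by the protocol's own description?** No. On a call, setting a new plan is one option beside problem-solving, so a contact can add no plan. In a session, a plan can be replaced when a rating is low, so a contact can involve more than one.

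**3. Scheduled contacts before the six-month outcome** (Follow-Up row): baseline 1, calls at weeks 2, 4 and 8 make 3, the month 3 session 1, calls at months 4 and 5 make 2. Total 1 + 3 + 1 + 2 = 7, or 8 with the month 6 session. For a fully reached patient this count is set by the schedule, whereas the number of plans is not.

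**4. Is there a stated figure to reproduce?** No. The documents give no power or detectable effect for Aim 3.

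**5. Illustration of what a proxy could cost.**

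- From the documents: n = 337 per arm at six months (Power and Sample Size Considerations); two-sided 5% level.
- Assumed: correlation of plan count with outcome 0.20; correlation ρ of contacts with plans from 0.9 to 0.3; contacts affect the outcome only through plans, so that the contact-outcome correlation is r = 0.20 × ρ.
- Formula (Fisher z): m = atanh(r) × √(337 − 3), with √334 = 18.28. Power = Φ(m − 1.96) + Φ(−m − 1.96).

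| Exposure | r | m | Power |
|---|---|---|---|
| Plan count itself | 0.20 | 3.71 | 96% |
| Contacts, ρ = 0.9 | 0.18 | 3.33 | 91% |
| Contacts, ρ = 0.7 | 0.14 | 2.58 | 73% |
| Contacts, ρ = 0.5 | 0.10 | 1.83 | 45% |
| Contacts, ρ = 0.3 | 0.06 | 1.10 | 20% |

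**6. How wide should the range for ρ be?** A simulation with 8 scheduled contacts by month 6, using assumed rates of reaching patients and of plans per contact, gave correlations from 0.94 to 0.28. The high end arises when about 90% of contacts yield a plan with little variation between patients. The low end arises when the plan rate varies widely between patients. The documents do not say which case applies.

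**The case against.** The strongest reply is that contacts are a reasonable measure of what Aim 3 is about. The aim's broader term is the amount of follow-up counseling, and the design section speaks of touch points in the same sentence as action plans. That section also makes action-planning a stated purpose of the calls. The counseling row has the patient create a plan for the coming week, while contacts are at least two weeks apart, so plans would ordinarily be due for renewal. If nearly every contact yields a plan, contacts and plans rank patients almost alike. Contacts also deliver chapter review, motivational interviewing and problem-solving, so they may affect outcomes by routes other than plans.

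Much of this stands, and it rules out three stronger readings that a reader might infer:

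- *Aim 3 goes wholly unanswered.* Not supported: contacts measure touch points directly and so inform the gradient half.
- *Many contacts add no plan.* Not supported: the text shows only that a call need not add one, not how often that happens.
- *Contacts are a diluted proxy with a known loss of power.* Not supported: every correlation in the table is assumed. If contacts also work by other routes, they could relate to outcome more strongly than plans do.

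A plan count is not a clean dose either. A new plan follows a low confidence or importance rating, so a high count may mark patients who are struggling.

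None of this turns a result in contacts into a minimum number of plans. That session content is logged shows that a plan count is feasible, not that it is planned.

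**Conclusion.** The mismatch is explicit, and nothing elsewhere in the documents resolves it. As written, the Aim 3 models inform the touch-point gradient but cannot give the minimum number of action plans. This conclusion rests on the text alone.

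The size of any power loss is unknown. Under the stated assumptions it runs from small (96% to about 91%) to large (96% to 20%), and it should be read only as an illustration.

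Aim 3 is a non-randomised association within one arm. The primary HbA1c comparison, the intent-to-treat principle and the sample size are untouched. The change is worth making because a stated aim is otherwise not analysed as worded.

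**What to change.** 1. In the Aim 3 paragraph of Data Analysis, add the number of action plans set before the outcome time point as an exposure alongside contacts and minutes. Use the number of plans completed as a second version.
2. Add two coded fields per contact to the coach tracking log: new plan set (yes/no) and previous plan completed (yes/no). Where coaching has started, back-code them from the session content and monthly EHR notes already kept.
3. State that the result is a non-randomised, within-arm association and that a high plan count may also mark patients who are struggling.
4. If plan counts cannot be recovered, reword Aim 3 and the matching sentence in Study Design and Procedures in terms of contacts and contact time, and draw no conclusion about a minimum number of plans.

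A separate limit remains. The Aim 3 model is linear in the dose, so a plan count entered that way gives a slope. A claim about a threshold would also need a pre-specified threshold or non-linear term.

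**Cost:** two log fields, a sentence or two in the analysis section, and some back-coding. The upper bound for back-coding is 375 patients × 14 scheduled contacts (5 in person, 9 by phone) = 5,250 contacts, if all were reached and all had already taken place. For the six-month outcome alone it is 375 × 7 = 2,625.

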Diabetes Distress. The Diabetes Distress Scale (DDS) is a 17-item measure of diabetesrelated emotional distress. It has four subscales corresponding to emotional burden, physicianrelated distress, regimen distress, and diabetes interpersonal distress.

Quality of Life. Patient-Reported Outcomes Measurement Information System (PROMIS) physical health (function) short form along with the PHQ-9 Depression Scale will be collected. Nurses will be notified if patients' scores indicate the need for follow-up either by the PCP or PCBHF, based on existing clinic protocol.

Clinical Outcomes

Hemoglobin A1c (HbA1c) and LDL cholesterol lab values, along with systolic and diastolic blood pressure values are collected as part of routine clinical care approximately every 3 months, and will be recorded from the medical record following each visit. *Body Mass Index.* Height and weight will also be taken from the medical record and the standard calculation for BMI applied (kg/m²). In addition, weight (in lbs.) will be recorded separately for weight gain/loss as an additional outcome.

Health Services Use

We will ask patients to self-report emergency department/urgency care visits, and hospitalizations. Dates of clinic appointments during the study period may be recorded from the medical record.

Fidelity outcomes:

Receipt of Diabetes Materials

We will ask patients whether they received all of the diabetes materials (yes/no), and if they still have them at each follow-up encounter (3 and 6 months).

Receipt of nurse/health coach counseling

We will ask patients to self-report whether their health coach/nurse reviewed the diabetes materials and/or provided counseling. Using health coach logs, we will document for each follow-

up time interval, whether the patient was reached (yes/no), and if yes, the time spent with the patient.

Provider-Patient Communication

We will ask questions adapted from the Consumer Assessment of Health Providers Survey (CAHPS)⁴¹ to evaluate the extent and quality of nurse/health coach counseling.

Perceived Helpfulness

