Baseline characteristics and demographics will be summarized overall and by clinic using descriptive statistics (mean \pm standard deviation for continuous variables, frequencies and percentages for categorical variables, and medians/quartiles as appropriate for ordinal variables). Analyses across all relevant outcomes (i.e., those corresponding to H₁-H₆) will mirror one another in general, with primary outcome being defined as HbA1c levels at six months. Secondary outcome measures include disease and treatment knowledge scores, self-efficacy scores, adherence to self-care behaviors, diabetes-related distress, diabetes-related quality of life and other clinical outcomes (blood pressure, LDL, cholesterol, BMI). Survey data will be collected at baseline, 3 and 6 months; clinical data will be collected at baseline, 3, 6, 9, and 12 months. The primary time point of interest for H₁-H₅ is three-month follow up and for clinical outcomes (H₆) is six-month follow-up, but subjects will be followed through 12 months in order to examine sustainability. We will assume missing data are missing at random, and analyses will consist of parametric statistical tests. Relevant statistical assumptions will be assessed as appropriate, and nonparametric analyses and/or transformations of variables will be explored in the event of violations.

Aim 1 analysis for each outcome will consist of an analysis of covariance (ANCOVA) in which overall mean (μ) follow-up outcome (e.g., HbA1c at 6 months) across groups will be modeled as follows:

$$\mu_i = \beta_0 + \beta_1 I(ACP intervention_i) + \beta_2 (Baseline_i) + \epsilon_i,$$

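### Aim 3 does not limit the count of coach contacts to those before the outcome, so a full-year count would include contacts that follow the 3- and 6-month outcomes

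*Combined protocol and SAP*

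**What the plan says.** The Aim 3 paragraph of Data Analysis uses only the intervention arm. It relates the "number of contacts with each subject and (b) length of contact time, with each relevant outcome variable" (H1-H6) "at follow-up via a linear model as above". It attaches no period to either exposure and names no month for the outcome.

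The time points come from elsewhere in the same section. "The primary time point of interest for H₁-H₅ is three-month follow up and for clinical outcomes (H₆) is six-month follow-up", and the models that Aim 3 refers back to are also run at "12-month follow-up (to examine sustainability").

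The table comparing the two arms, in Study Design and Procedures, sets the contact schedule: calls at weeks 2, 4 and 8, in-person sessions at about months 3, 6, 9 and 12, and "Monthly post-visit phone calls between clinic visits after 3 months (4,5,7, 8, 10, and 11 month calls"). Its Clinical Integration row gives the coach the patient's "HbA1c lab value at visit) prior to patient counseling session". The text of that section describes touch points spread over one year, and says that Aim 3 looks for the smallest number of action plans needed to reach clinical goals.

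The contact data would support a time window. Under Receipt of nurse/health coach counseling: "Using health coach logs, we will document", for each follow-up interval, whether the patient was reached and for how long. The coach training described under Preparation phase covers a tracking system for the number and length of contacts.

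**The concern.** A dose should precede the response that it is meant to explain. Read literally, each subject's number of contacts is the whole year's count, and no other section narrows it. For the 3- and 6-month outcomes, part of that count is still to come when the outcome is measured.

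Two things can then go wrong. If late contacts have nothing to do with the earlier outcome, they add noise to the exposure and flatten a real dose slope. If they do depend on it, the slope partly measures the effect of the outcome on contact. There are routes for this: the coach sees HbA1c before the session, and patients must be reachable and willing for a contact to happen.

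What is at stake is the answer on how much counseling is needed, which is the purpose of Aim 3. An open window also leaves a choice that could be made after results are seen.

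**Working it through.** The plan gives no total of contacts and no share falling after an outcome, so there is no figure of its own to reproduce.

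**Step 1. Count the schedule.** Inputs: the Follow-Up row of the comparison table, and the baseline coach meeting under Recruitment.

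- Total = 1 baseline + 3 early calls + 4 quarterly sessions + 6 later calls = 14.
- Before month 3: baseline and weeks 2, 4, 8 = 4.
- Before month 6: those 4, plus month 3 and months 4 and 5 = 7.

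| Outcome time | Strictly after | With same-visit session |
|---|---|---|
| 3 months | 9/14 = 64% | 10/14 = 71% |
| 6 months | 6/14 = 43% | 7/14 = 50% |
| 12 months | 0/14 | 1/14 = 7% |

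Leaving out the baseline session (13 contacts) gives 69-77% at 3 months and 46-54% at 6 months. For contact time, call length is not stated. Assuming 5-15 minutes per call and a baseline session of 15 or 30 minutes (or left out), 56-86% of minutes follow a 3-month outcome and 37-62% a 6-month outcome, over both treatments of the same-visit session.

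**Step 2. Dilution when later contacts are unrelated to the outcome.** From the plan: 337 patients per arm at 6 months. Assumed: residual SD 1.3, each contact kept with probability 0.7, early and late contacts independent, true slope -0.10 HbA1c points per pre-outcome contact.

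- Variance of the earlier count (baseline always kept, 6 others): 6 x 0.7 x 0.3 = 1.26.
- Variance of the later count (7, including the same-visit session): 7 x 0.7 x 0.3 = 1.47.
- Dilution factor: 1.26 / (1.26 + 1.47) = 0.46, so the expected slope is -0.10 x 0.46 = -0.046.
- Earlier count only: SE = 1.3 / sqrt(337 x 1.26) = 0.063; z = 0.10 / 0.063 = 1.59; power about 35%.
- Full count: SE about 1.3 / sqrt(337 x 2.73) = 0.043; z = 0.046 / 0.043 = 1.07; power about 19%.

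Simulation gives -0.044, and power falling from 35% to 18%.

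**Step 3. False positives at 6 months when later contact depends on the outcome.** Same assumptions, no true dose effect, follow-up HbA1c regressed on baseline and count. The odds ratio (OR) is for keeping each later contact, per 1-point higher HbA1c.

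| Assumed OR | Full count, share significant at 5% |
|---|---|
| 1.00 | 5% |
| 0.98 | 7% |
| 0.95 | 21% |
| 0.90 | 61% |
| 0.85 | 92-96% |
| 0.70 | 100% |

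Allowing patients to differ in engagement (SD 0.7 to 1.0 on the logit scale) lowers the 0.85 result to 60-41%. Counting only earlier contacts stays near 5% throughout.

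A second setup assumes baseline correlation 0.5 and engagement SD 0.7, and puts the same-visit session on the earlier side. Feedback is expressed as the rise in log-odds of a later contact per SD of better response.

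| Feedback | 3-month outcome, full count | 6-month outcome, full count |
|---|---|---|
| 0 | 5% | 6% |
| 0.15 | 53% | 27% |
| 0.30 | 98% | 75% |
| 0.50 | 100% | 99% |

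The windowed count rejects in 4.6-5.2% of runs in every case.

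**Step 4. Direction.** If coaches instead pursue poorly controlled patients (OR 1.15), the first setup gives a slope of about +0.13 per contact with no true effect, an apparent harm. With a true slope of -0.10 and OR 1.05, the full-count slope is about zero.

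**The case against.** The strongest reply is that the plan never says the contacts are totalled over 12 months. Coach logs are kept by follow-up interval, so a count matched to each outcome would be a natural way to carry out the analysis. This stands as far as it goes: a reader might infer that a 12-month total is planned, but the text is only silent on the window. It does not remove the point, because nothing in the plan requires the matched count, and the aim is framed around touch points over a year.

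Other stronger readings also fail:

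- **At least half of the dose follows the outcome.** True for 3-month outcomes. For the 6-month HbA1c it is 43%, and reaches 50% of the 14 only if the same-visit session is included.
- **Every Aim 3 result is affected.** Twelve-month clinical outcomes have essentially no later contacts.
- **Timing alone creates a false dose-response.** Without feedback the false-positive rate stays at 5-6%.
- **A false benefit is nearly certain.** The rates above 90% rest on assumed feedback. The documents give a route for feedback but neither its size nor its sign.

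Finally, Aim 3 is an association analysis within one arm. The randomized comparison and the primary analysis are untouched.

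**Conclusion.** The concern holds as an undefined exposure window. If all contacts are counted, 64% of the scheduled dose (71% with the same-visit session) comes after a 3-month outcome, and 43% (50%) after the 6-month HbA1c. These shares rest only on the schedule.

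The consequences rest on assumptions. A full count cuts a true slope to a little under half if late contacts are independent of early ones. If late contact responds to the outcome, the slope is biased toward apparent benefit or apparent harm, with false-positive rates anywhere from about 5% to over 90%. Contact completion, spread of engagement and feedback are not given in the documents, so no single rate should be quoted as the expected error.

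A window restores the time order and no more. Contact is not randomized. If engagement raises the log-odds of contact by 0.5 per SD and independently lowers HbA1c by 0.3 per SD (both assumed), the windowed model still rejects in about 50% of trials with no true dose effect.

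**What to change.** In the Aim 3 paragraph of Data Analysis, add: *For each outcome and time point, exposure is the number of health coach contacts, and the minutes of contact, dated before that outcome's sample, measurement or interview. The session held at the same visit is not counted.* Use actual dates, because visits are only approximately quarterly.

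The scheduled maximum is then 4 contacts for 3-month outcomes, 7 for 6-month outcomes and 14 - 1 = 13 for 12-month clinical outcomes.

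Add a second sentence stating that Aim 3 results are observational associations and may reflect patient engagement as well as counseling.

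The cost is a date filter on coach logs already planned, with no new data and no change to patient care. The price is a narrower dose range: with at most 4 or 7 contacts instead of 14, the 3- and 6-month analyses cannot speak to thresholds above those numbers.
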